4. For patients with epilepsy and a history of seizures, the Epilepsy Seizures Diary is to be dispensed to the parent at each visit and completed only on the days that the patient has a seizure, which should include the date, time, duration and type of the seizure ([Appendix 10](#)). The Epilepsy Seizures Diary is to be completed only by the patient's parent/caregiver after each seizure and to be entered into the electronic case report form (eCRF) by the site at each study visit.

5. The TESS ([Appendix 5](#)) and CGAS ([Appendix 9](#)) must be administered and completed by the Investigator with the parent/caregiver's input at the study visit indicated.

6. Sleep and Nap Diary is to be completed 14 nights before each scheduled visit ([Appendix 1](#) and [Appendix 2](#)). The parent will complete the questionnaire either directly into the eCRF or on the printed version. If the printed version is used, at a later time point, the site coordinator will enter the questionnaire data into the eCRF. At the screening visit, the Sleep and Nap Diary is dispensed. The study coordinator/Investigator must provide guidance to the parents on how to complete the diary by reviewing the diary question by question and explaining the importance of completing all required data entry every morning, preferably within 2 to 3 hours after the patient wakes up. It is critical that the study coordinator/Investigator provide a thorough review and explanation of the diary to the parents to ensure that the data retrieved is high quality and reliable. A follow-up phone call to remind patients to begin filling out Sleep and Nap Diaries will be made every week before Visits 1 and 2, as well as every week during the study period up to Visit 7. Between Visits 7 and Visit 8, the phone call will be made once a month.

7. CSDI ([Appendix 6](#)), SDQ ([Appendix 8](#)), ESS ([Appendix 7](#)), WHO-5 ([Appendix 9](#)), and PSQI ([Appendix 8](#)) are to be completed by the site coordinators/Investigators with the parents/caregiver, by posing the questions in the questionnaires and filling in the responses given by the parents/caregiver. Note: The ESS, WHO-5, and PSQI are to assess sleepiness, quality of sleep, and well-being of the parent/caregiver's and NOT the child.

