8.1 SCREENING VISIT (DAY 1 AT -4 WEEKS ±3 DAYS)

These items may be carried out by the Investigator or a qualified designee:

- Explain the conduct of the study.
- Provide the informed consent form (ICF) and information sheet to patients and legal guardians to read and sign.
- Eligibility screening done by Investigator or a qualified designee:
- Record detailed medical history.
- Record of demographic data.
- Verify sleep problem based on completed diaries.
- Perform physical examination and measure vital signs.
- Measure body weight and height for the BMI and Z-score calculations.
- Review inclusion/exclusion criteria.
- Administer urine dipstick pregnancy tests to females of child-bearing potential.
- Explain sleep hygiene training and dispense training booklet.
- Explain and dispense the Sleep and Nap Diary (to be completed during the 14 nights before Visit 1; [Appendix 1](#)). The study coordinator/Investigator must provide guidance to the parents on how to complete the diary by reviewing the diary question by question and explaining the importance of completing all required data entry every morning, preferably within 2 to 3 hours after the patient woke up. It is critical that the study coordinator/Investigator provide a thorough review and explanation of the diary to the parents to ensure that the data retrieved is high quality and reliable. Please also refer to [Appendix 2](#) (Sleep and Nap Diary Guidelines, Presentation and Take-Home Instructions for Parents).

- Explain and dispense Epilepsy Seizures Diaries for patients diagnosed with epilepsy ([Appendix 10](#); to be completed by the parent/caregiver after each seizure).
- The visit should be carried out within ± 3 days.

During the screening period, if a parent does not complete the diary appropriately due to a misunderstanding, then with the Investigator's approval, a patient can be re-screened.

8.2 PRE-VISIT 1

A follow-up phone call to remind patients to begin filling out Sleep and Nap Diaries will be made every week before Visits 1 and 2, as well as every week during the study period up to Visit 7. The site is to make a phone call at 2 weeks ahead of Visit 1 to remind patients to begin filling out Sleep and Nap Diaries. If sleep hygiene was not required (i.e., the patient entered the study with history of documented sleep hygiene at Visit 1), no call will be needed, as Visit 1 will be the first visit and serve as the screening visit.

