12.8.3 Exploratory Endpoints

The changes in BMI and Z-score from baseline to the end of the study will be summarized using shift tables showing the number of children below, within and above z calculated normal at each treatment group, separately. The-BMI and Z-scores are designed to take into account the amount of weight gain that would be expected due to normal growth in children and adolescents. The BMI and Z-scores are categorized by age and gender standardized values (corresponding to a normal distribution with mean 0 and a SD of 1) of the actual weight measurements, based on the Growth Charts provided by the Centers for Disease Control.

Tanner scores for pubertal assessment in children ≥ 8 years of age during the study will be analyzed using the web application (<http://vps.stefvanbuuren.nl/puberty>)²⁰. This tool calculates SD scores of individual observations of Tanner scores and additionally plots those scores in stage line diagram²¹.

Descriptive statistics will be provided for head and height measurements and changes in head and height measurements from baseline to Week 108 in children ≤ 5 years of age.

Descriptive statistics will also be provided for the number and severity of epilepsy seizures in children diagnosed with epilepsy, using the Epilepsy Seizures Diaries that are completed by parents at the time of the seizures and entered in the eCRF at a later time point by the site.

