Appendix 10: Epilepsy Seizures Diary

This is to be completed only by the patient's parent/caregiver after each seizure.

Site:	
Subject number:	
NEU_CH_7911 - Epileptic Seizure Diary	
	
Did the child have any seizures since the last visit?	 Yes  No
If yes, please provide details for all seizures	
Date of seizure	
Day or Night	 Day  Night
Duration of seizure (minutes)	
Seizure type	 G1 - absence seizure  G2 - myoclonic seizure  G3 - atonic seizure  G4 - tonic seizure  G5 - clonic seizure  G6 - tonic-clonic convulsion  G7 - other with unconsciousness  F1 - aura  F2 - other with consciousness retained
Was emergency medication given?	 Yes  No
If yes, please provide details for all seizures	
Date of seizure	
Day or Night	 Day  Night
Duration of seizure (minutes)	
Seizure type	 G1 - absence seizure  G2 - myoclonic seizure  G3 - atonic seizure  G4 - tonic seizure  G5 - clonic seizure

Site:

Subject number:

NEU_CH_7911 - Epileptic Seizure Diary

	 G6 - tonic-clonic convulsion  G7 - other with unconsciousness  F1 - aura  F2 - other with consciousness retained	
Was emergency medication given?	 Yes  No	
If yes, please provide details for all seizures		
Date of seizure		
Day or Night	 Day  Night	
Duration of seizure (minutes)		
Seizure type	 G1 - absence seizure  G2 - myoclonic seizure  G3 - atonic seizure  G4 - tonic seizure  G5 - clonic seizure  G6 - tonic-clonic convulsion  G7 - other with unconsciousness  F1 - aura  F2 - other with consciousness retained	
Was emergency medication given?	 Yes  No	
Final version: 2014-03-07 (1.000.002.000)	CONFIDENTIAL	Neurim Pharmaceuticals Ltd.

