- To assess the treatment effect of Circadin® 2/5/10 mg on pubertal status using the Tanner scale in children ≥ 8 years of age. For children ≤ 5 years of age, only height and head circumference will be used to stage children development. Between the age of 5 and 8 the children's physical development will be determined using the BMI (baseline through Week 108)
- In children diagnosed with epilepsy, to compare the effect of Circadin® 2/5 mg to that of placebo on the number and severity of epilepsy seizures during double-blind treatment and to assess the effect of Circadin® 2/5/10 mg during the open-label period using seizure diaries

4 Endpoints

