4.3 Exploratory Endpoints

- Sleep variables as assessed by the Sleep and Nap Diary at baseline (Week 2), after 3 weeks of double blind treatment (Week 5), and after 13, 26, and 39 weeks of open-label treatment (Weeks 28, 41, and 54)
- Sleep disturbance as assessed by the CSDI score at baseline after 3 weeks of double-blind treatment (Week 5), after 13, 26, 39, and 91 weeks of open-label treatment (Weeks 28, 41, 54, and 106, respectively), and at the end of study visit (Week 108)
- Social functioning at home, in school, and in community settings as assessed by the CGAS after 13 weeks (Week 28) of open-label treatment
- Behavior at home and in school as assessed by the SDQ after 13 weeks (Week 28) of open-label treatment
- Caregiver's daytime sleepiness (i.e., NOT the child's) during the study as assessed by the ESS (Weeks 0, 2, 5, 15, 28, 41, 54, 106 and 108)
- Caregiver's well-being (i.e., NOT the child's) during the study as assessed by the WHO-5 questionnaire (Weeks 0, 2, 5, 15, 28, 41, 54, 106 and 108)
- Caregiver's quality of sleep at night (i.e., NOT the child's) during the study using the PSQI global score and components (at Weeks 0, 2, 5, 15, 28, 41, 54, 106 and 108)
- Dosage received by visit and maximum dosage received overall
- BMI and Z-score assessed during the study
- Pubertal assessment using the Tanner scale during the study. The Tanner scale will be used to assess and stage physical development in children ≥ 8 years of age. For children ≤ 5 years of age, only height and head circumference will be used to stage children development. Between the age of 5 and 8, the children's physical development will be determined using BMI.
- In children diagnosed with epilepsy, the number and severity of epilepsy seizures assessed during the study using seizures diaries completed by the parents at the time of the seizures

5 Study Design

This is a randomized placebo-controlled study in children diagnosed with Autism Spectrum Disorders and neurodevelopmental disabilities caused by neurogenetic diseases. Children will have a documented history of these disorders, as confirmed or consistent with the International Classification of Diseases (ICD-10) or Diagnostic and Statistical Manual of Mental Disorders, Fifth Edition, Text Revision (DSM-5/4) criteria, having International Classification of Sleep Disorders (ICSD) criteria-based sleep disturbances modified to take into account the uniqueness of insomnia in the pediatric population at screening.

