12.7 Epilepsy

Number and type of epilepsy seizures in children diagnosed with epilepsy will be tabulated, using the Epilepsy Seizures Diaries that are completed by parents at the time of the seizures. For the number of epilepsy seizures, percentages will be based on the number of children diagnosed with epilepsy.

The median number of epilepsy seizures will be summarized by scheduled visit and across all visits. At each visit Wilcoxon rank-sum test will be performed to compare the number of seizures occurring between the two groups.

Example SAS code for this analysis is given below:

```
proc NPAR1WAY data=epil wilcoxon;  
  class trtp;  
  var numepil;  
  exact wilcoxon;  
run;
```

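### SAP 12.7 tests raw seizure counts between arms at every visit, without the pre-randomisation diary or days observed, and leaves the named severity endpoint without a diary-based summary

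*SAP*

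**What the plan says.** SAP 12.7 covers the seizure diary. It first says: "Number and type of epilepsy seizures in children diagnosed with epilepsy will be tabulated". It then summarises the median count by scheduled visit and across all visits, and adds the test: "At each visit Wilcoxon rank-sum test will be performed to compare the number of seizures occurring between the two groups". The example code is a rank-sum procedure with treatment as the class variable and the seizure count as the only analysis variable; an exact test is requested. The shells, Tables 14.3.8.1 to 14.3.8.3, cover number, the Wilcoxon test and type.

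The aims are wider. The exploratory objective in SAP 3.3 is a comparison with placebo "on the number and severity of epilepsy seizures during double-blind treatment". The endpoint in SAP 4.3 is "the number and severity of epilepsy seizures assessed during the study using seizures diaries". Protocol 12.8.3 says: "Descriptive statistics will also be provided for the number and severity of epilepsy seizures in children diagnosed with epilepsy".

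On data collection, the protocol's screening visit (8.1) includes the step "Explain and dispense Epilepsy Seizures Diaries for patients diagnosed with epilepsy", and Table 5-2, footnote 4 adds that "the Epilepsy Seizures Diary is to be dispensed to the parent at each visit". Diaries are collected at Visits 1 and 2, before randomised treatment starts. The form in protocol Appendix 10 asks for events since the last visit and records date, day or night, duration and type. It also asks: "Was emergency medication given".

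**The concern.** There are three separate problems.

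- **Comparison.** Children with epilepsy can differ widely in seizure frequency. A test on follow-up counts alone leaves all of that variation in the noise, although each child's own earlier diary is available. In a small subgroup, one or two children with frequent seizures falling into the same arm can also hide or mimic an effect.
- **Scope.** The objective is drug against placebo in the double-blind phase. The test is not limited to that phase.
- **Severity.** It is named in the objective, the endpoint and the protocol's analysis section, but the diary analysis stops at number and type.

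The question is one of harm. A weak test that comes out non-significant is easily read as reassurance.

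**Working it through.** **No planned figure to reproduce.** The documents give no sample size or power for the seizure comparison. The stated 45 per group concerns total sleep time and plays no part here.

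**Objective against analysis**

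| Item | Objective, endpoint, protocol 12.8.3 | SAP 12.7 and Tables 14.3.8.1–3 |
|---|---|---|
| Number | yes | yes |
| Severity | yes | no |
| Type | not named | yes |
| Comparison with placebo | double-blind phase (SAP 3.3) | every visit |

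SAP section 14 lists one change, the move of the CSDI to a secondary endpoint.

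**Counting windows**, from protocol Table 5-1 (weeks × 7):

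- Visit 2 to 3: 3 × 7 = 21 days
- Visit 3 to 4: 10 × 7 = 70 days
- Visits 4 to 5, 5 to 6 and 6 to 7: 13 × 7 = 91 days each
- Visit 7 to 8: 52 × 7 = 364 days
- Visit 8 to end of study: 2 × 7 = 14 days

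That makes seven post-randomisation visits. Only Visits 3 and 4 compare drug with placebo. At the other 7 − 2 = 5, both arms have had the same type of treatment: Circadin at four, placebo run-out at the last. SAP 9.2 nevertheless groups open-label tables by randomised arm. The across-visits median adds windows from 14 to 364 days.

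**Baseline windows.** A child who needs sleep-hygiene training has 4 + 2 = 6 weeks of diary before Visit 2. A child who enters directly at Visit 1 has about 2 weeks. A baseline count must therefore be expressed per day. SAP 9.3 defines a baseline for all safety variables as the last value before randomised treatment, but 12.7 does not use it.

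**Size of the precision loss (illustration).** None of the following inputs is in the documents. Assumed: 12 children with epilepsy per arm (12/60 = 20% of each arm of 120/2) and a true 2.5-fold increase. Counts are Poisson, with gamma variation between children. The raw test is a Wilcoxon on the follow-up count. The adjusted test is a Wilcoxon on the residuals from regressing follow-up rank on baseline rank. Except in the last row, the mean is 1 seizure per week, the between-child CV is 1, the baseline is 4 weeks and follow-up is 13 weeks (21 + 70 = 91 days).

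| Further assumption | Raw | Adjusted |
|---|---|---|
| No extra within-child variation | 41% | 80% |
| Within-child CV 0.5 | 35% | 51% |
| Within-child CV 0.7 | 30% | 38% |
| Rare seizures: half the children seizure-free, the rest 0.2 per week, within-child CV 0.7, 2-week baseline, 10-week window | 8% | 8% |

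With about 2,000 simulated trials per setting, the Monte Carlo standard error is at most √(0.5 × 0.5/2000) = 1.1 points. With no effect, rejection stayed near 4–5%. The simulations used asymptotic p-values, whereas the SAP code also asks for exact ones.

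**Early leavers (conditional).** Suppose that part-window counts are included in the Visit 4 test, 10% of placebo and 50% of active children leave part-way, and there are 12 per arm with a mean of 2 seizures per week (between-child gamma shape 1, within-child shape 4, 70-day window). With no effect, the raw count rejects in 7.7% of trials and the per-day rate in 4.1%. For a doubled rate, power is 8.7% with the raw count, 18.8% per day, and 45.1% per day relative to baseline. At 10% against 30% leaving, the false-positive rates are 4.9% and 4.4%.

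**Limit of any rank test.** The smallest two-sided exact p-value is 2/C(6,3) = 2/20 = 0.10 with 3 per arm and 2/C(8,4) = 2/70 = 0.029 with 4.

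**The case against.** The strongest reply is that this is an exploratory safety endpoint for which protocol 12.8.3 promised only descriptive statistics. Under randomisation an exact rank-sum test is valid without adjustment, and the gain from adjustment depends on unknown seizure rates. All of that stands, and it limits the weight of the point.

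A reader might infer that 12.7 is the only check for worsening epilepsy. It is not. TESS item 8 grades seizures 0 to 3, and a new symptom or a worsening from Visit 1 becomes an adverse event. Adverse events are tabulated by arm and severity, and a DSMB reviews safety data. SAP 12.7 is, however, the only planned between-arm test of diary seizures.

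A reader might also infer that early leavers will look better. The SAP does not say whether a withdrawal-visit count is assigned to a scheduled visit. Within one visit the nominal window is the same in both arms, so the distortion is possible but not established.

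The baseline is imperfect. Its length differs between children, and for some it overlaps wash-out of prohibited drugs, a list that includes benzodiazepines and phenobarbital. The diary also has no severity grade, so any severity summary needs a definition. These points affect how the fix is specified; they do not justify leaving the baseline and severity out.

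**Conclusion.** The point holds as a moderate one. Two parts rest on the text alone: severity is named in three places and has no diary-based table, with no entry in section 14; and the test as worded extends to visits that cannot compare drug with placebo.

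The third part, unused baseline and exposure, costs precision and protection against chance imbalance. It does not make the test invalid when follow-up is equal. In the settings examined, the gain in power at 12 per arm runs from nil to about 39 points (80 − 41), with no loss in any of them. No single figure can be claimed, because the size of the epilepsy subgroup and the seizure rates are not in the documents. With 3 or fewer per arm, no exact rank test reaches 5% under either approach. The primary result is unaffected.

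**What to change.** Revise SAP 12.7 as follows.

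1. Make the between-arm comparison one double-blind analysis, Visit 2 to Visit 4, of seizures per diary-day, adjusted for the baseline rate per day by rank ANCOVA. This is preferable to a negative binomial model, which the subgroup may be too small to support. Define baseline as all diary days before randomisation, and say that this replaces the last-value rule of SAP 9.3 for this variable. A sensitivity run on the two run-in weeks alone would show whether wash-out matters.
2. State how counts and days from withdrawal visits enter the analysis.
3. Present open-label and run-out visits descriptively, as rates.
4. Tabulate seizure duration and emergency-medication use alongside type as the severity summary, and add a shell to the 14.3.8 series.
5. Record in section 14 the added test and the severity definition.

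The cost is SAP wording and minor programming, with no new data collection. The remaining downside is the unequal baseline, which for some children overlaps wash-out.

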12.8 Other Data

12.8.1 Pregnancy Test

All subjects will be tested for pregnancy by urine dipstick at Screening, Week 2, Week 15 and Week 108. Details of pregnancy test results will be listed.

12.8.2 Physical Examination

Physical examination will be assessed at screening each visit including the placebo run-out (withdrawal) period. Physical examination findings at screening will be classified using standard categories as listed on the Medical History eCRFs. Any physical examination finding that is judged by the Investigator as a clinically significant change (worsening) compared to a baseline value (Visit 2) will be considered an AE and recorded on the adverse event eCRF. The date of the physical examination will be listed.

12.8.3 Visit Dates

Visit dates will be listed.

13 Interim Analysis

All results will be summarized at the end of the first open-label period (Week 28; Visit 5), and will be submitted in the form of a clinical study report (CSR) to the regulatory authorities for evaluation of approval of the study drug for use in the investigated population. This will constitute the final analysis of data up to that point and no statistical adjustment of significance tests is required.

The data from the second open-label period will be summarized on the completion of the study and reported as an appendix to the CSR.

14 Changes to Planned Methodology

The analysis of total CSDI score at 13 weeks has been moved from an exploratory endpoint to a secondary endpoint to reflect the greater importance being placed on this endpoint at the present time.

15 References

- [1] Kenward, M. G. and Roger, J. H. (1997), Small Sample Inference for Fixed Effects from Restricted Maximum Likelihood, *Biometrics*, 53, 983–997
- [2] Ratitch, B. and O’Kelly, M. (2011), Implementation of Pattern-Mixture Models Using Standard SAS/STAT Procedures, in *Proceedings of PharmaSUG 2011 (Pharmaceutical Industry SAS Users Group)*, SP04, Nashville.
- [3] Rubin, D. B. (1987), *Multiple Imputation for Nonresponse in Surveys*, New York: John Wiley & Sons.

16 Tables, Figures and Listings

Tables and listings will be presented landscape. A font size of 8 and a font of courier new will be used throughout for tables and listings. Tables and listings will be provided as a bookmarked pdf. Figures will be provided as individual files.

The subject population being utilized in the table will be indicated in the table title. Page numbers and dates of production will be included in an appropriate place at the bottom of the output. Listings which support the table will also be detailed in an appropriate place at the bottom of the output.

Tables will only be generated where there is sufficient data to warrant the inclusion of the table.

16.1 List of Tables

Table Number	Table Title	Population
Table 14.1.1.1	Patient Disposition: Double Blind Phase	All Enrolled Set
Table 14.1.1.2	Patient Disposition: First Open Label Phase	All Enrolled Set
Table 14.1.1.3	Patient Disposition: Second Open Label Phase	All Enrolled Set
Table 14.1.2.1	Demographic Characteristics	All Enrolled Set
Table 14.1.2.2	Demographic Characteristics	All Randomized Set
Table 14.1.3	Baseline Characteristics	All Randomized Set
Table 14.1.4	Diagnosis of Neurodevelopmental Disability	All Randomized Set
Table 14.1.5	Melatonin Use	All Randomized Set
Table 14.1.6	Medical History	All Randomized Set
Table 14.1.7	Prior Medications	All Randomized Set
Table 14.1.8	Concomitant Medications - Double Blind Phase	All Randomized Set
Table 14.1.9	Concomitant Medications - First Open Label Phase	All Randomized Set
Table 14.1.10	Concomitant Medications - Second Open Label Phase	All Randomized Set
Table 14.2.1.1	Number of Sleep and Nap Diaries with Data Recorded	FAS Set
Table 14.2.1.2	Number of Sleep and Nap Diaries with a Valid TST	FAS Set
Table 14.2.1.3	SND Total Sleep Time and Change from Baseline – Double Blind - Descriptive Statistics	FAS Set
Table 14.2.1.4	SND Total Sleep Time Change from Baseline at 13 Weeks Double Blind – MMRM Analysis	FAS Set
Table 14.2.1.5	SND Total Sleep Time Change from Baseline at 13 Weeks Double Blind – MMRM Analysis	Per Protocol Set
Table 14.2.1.6	SND Sleep Latency and Change from Baseline – Double Blind - Descriptive Statistics	FAS Set
Table 14.2.1.7	SND Sleep Latency Change from Baseline at 13 Weeks Double Blind – MMRM Analysis	FAS Set
Table 14.2.1.8	SND Sleep Latency Change from Baseline at 13 Weeks Double Blind – MMRM Analysis	Per Protocol Set

Table Number	Table Title	Population
Table 14.2.1.9	SND Duration of Wake and Change from Baseline – Double Blind - Descriptive Statistics	FAS Set
Table 14.2.1.10	SND Duration of Wake Change from Baseline at 13 Weeks Double Blind – MMRM Analysis	FAS Set
Table 14.2.1.11	SND Duration of Wake Change from Baseline at 13 Weeks Double Blind – MMRM Analysis	Per Protocol Set
Table 14.2.1.12	SND Number of Awakenings and Change from Baseline – Double Blind - Descriptive Statistics	FAS Set
Table 14.2.1.13	SND Number of Awakenings Change from Baseline at 13 Weeks Double Blind – MMRM Analysis	FAS Set
Table 14.2.1.14	SND Number of Awakenings Change from Baseline at 13 Weeks Double Blind – MMRM Analysis	Per Protocol Set
Table 14.2.1.15	SND Longest Sleep Period and Change from Baseline – Double Blind - Descriptive Statistics	FAS Set
Table 14.2.1.16	SND Longest Sleep Period Change from Baseline at 13 Weeks Double Blind – MMRM Analysis	FAS Set
Table 14.2.1.17	SND Longest Sleep Period Change from Baseline at 13 Weeks Double Blind – MMRM Analysis	Per Protocol Set
Table 14.2.1.18	SND Total Time in Bed and Change from Baseline – Double Blind - Descriptive Statistics	FAS Set
Table 14.2.1.19	SND Total Time in Bed Change from Baseline at 13 Weeks Double Blind – MMRM Analysis	FAS Set
Table 14.2.1.20	SND Total Time in Bed Change from Baseline at 13 Weeks Double Blind – MMRM Analysis	Per Protocol Set
Table 14.2.1.21	SND Quality of Sleep and Change from Baseline – Double Blind - Descriptive Statistics	FAS Set
Table 14.2.1.22	SND Quality of Sleep Change from Baseline at 13 Weeks Double Blind – MMRM Analysis	FAS Set
Table 14.2.1.23	SND Current Alertness and Change from Baseline – Double Blind - Descriptive Statistics	FAS Set
Table 14.2.1.24	SND Current Alertness Change from Baseline at 13 Weeks Double Blind – MMRM Analysis	FAS Set
Table 14.2.1.25	SND Feeling on Awakening and Change from Baseline – Double Blind - Descriptive Statistics	FAS Set
Table 14.2.1.26	SND Feeling on Awakening Change from Baseline at 13 Weeks Double Blind – MMRM Analysis	FAS Set
Table 14.2.1.27	SND Number of Naps and Change from Baseline – Double Blind - Descriptive Statistics	FAS Set
Table 14.2.1.28	SND Number of Naps Change from Baseline at 13 Weeks Double Blind – MMRM Analysis	FAS Set
Table 14.2.1.29	SND Duration of Naps and Change from Baseline – Double Blind - Descriptive Statistics	FAS Set
Table 14.2.1.30	SND Duration of Naps Change from Baseline at 13 Weeks Double Blind – MMRM Analysis	FAS Set
Table 14.2.2.1	CSDI Sleep Disturbance Total Score and Change from Baseline – Double Blind - Descriptive Statistics	FAS Set
Table 14.2.2.2	CSDI Sleep Disturbance Total Score Change from Baseline at 13 Weeks Double Blind – MMRM Analysis	FAS Set
Table 14.2.2.3	CSDI Sleep Disturbance Total Score Change from Baseline at 13 Weeks Double Blind – MMRM Analysis	Per Protocol Set
Table 14.2.2.4	CSDI Sleep Disturbance Problems Settling and Change from Baseline – Double Blind - Descriptive Statistics	FAS Set

Table Number	Table Title	Population
Table 14.2.2.5	CSDI Sleep Disturbance Problems Settling Change from Baseline at 13 Weeks Double Blind – MMRM Analysis	FAS Set
Table 14.2.2.6	CSDI Sleep Disturbance Time to Settle and Change from Baseline – Double Blind - Descriptive Statistics	FAS Set
Table 14.2.2.7	CSDI Sleep Disturbance Time to Settle Change from Baseline at 13 Weeks Double Blind – MMRM Analysis	FAS Set
Table 14.2.2.8	CSDI Sleep Disturbance Night Awakening and Change from Baseline – Double Blind - Descriptive Statistics	FAS Set
Table 14.2.2.9	CSDI Sleep Disturbance Night Awakening Change from Baseline at 13 Weeks Double Blind – MMRM Analysis	FAS Set
Table 14.2.2.10	CSDI Sleep Disturbance Time to Resettle and Change from Baseline – Double Blind - Descriptive Statistics	FAS Set
Table 14.2.2.11	CSDI Sleep Disturbance Time to Resettle Change from Baseline at 13 Weeks Double Blind – MMRM Analysis	FAS Set
Table 14.2.2.12	CSDI Sleep Disturbance Awakening Before 5am and Change from Baseline – Double Blind - Descriptive Statistics	FAS Set
Table 14.2.2.13	CSDI Sleep Disturbance Awakening Before 5am Change from Baseline at 13 Weeks Double Blind – MMRM Analysis	FAS Set
Table 14.2.2.14	CSDI Sleep Disturbance Co-Sleeping and Change from Baseline – Double Blind - Descriptive Statistics	FAS Set
Table 14.2.2.15	CSDI Sleep Disturbance Co-Sleeping Change from Baseline at 13 Weeks Double Blind – MMRM Analysis	FAS Set
Table 14.2.2.16	CSDI Sleep Disturbance Satisfaction and Change from Baseline – Double Blind - Descriptive Statistics	FAS Set
Table 14.2.2.17	CSDI Sleep Disturbance Satisfaction Change from Baseline at 13 Weeks Double Blind – MMRM Analysis	FAS Set
Table 14.2.3.1	CGAS Score and Change from Baseline – Double Blind - Descriptive Statistics	FAS Set
Table 14.2.3.2	CGAS Score Change from Baseline at 13 Weeks Double Blind – MMRM Analysis	FAS Set
Table 14.2.3.3	CGAS Score Change from Baseline at 13 Weeks Double Blind – MMRM Analysis	Per Protocol Set
Table 14.2.4.1	SDQ Total Difficulties Score and Change from Baseline – Double Blind - Descriptive Statistics	FAS Set
Table 14.2.4.2	SDQ Total Difficulties Score Change from Baseline at 13 Weeks Double Blind – MMRM Analysis	FAS Set
Table 14.2.4.3	SDQ Total Difficulties Score Change from Baseline at 13 Weeks Double Blind – MMRM Analysis	Per Protocol Set
Table 14.2.4.4	SDQ Impact Score and Change from Baseline – Double Blind - Descriptive Statistics	FAS Set
Table 14.2.4.5	SDQ Impact Score Change from Baseline at 13 Weeks Double Blind – MMRM Analysis	FAS Set
Table 14.2.4.6	SDQ Subscale Emotional Symptoms Score and Change from Baseline – Double Blind - Descriptive Statistics	FAS Set
Table 14.2.4.7	SDQ Subscale Emotional Symptoms Score Change from Baseline at 13 Weeks Double Blind – MMRM Analysis	FAS Set
Table 14.2.4.8	SDQ Subscale Conduct Problem Score and Change from Baseline – Double Blind - Descriptive Statistics	FAS Set
Table 14.2.4.9	SDQ Subscale Conduct Problem Score Change from Baseline at 13 Weeks Double Blind – MMRM Analysis	FAS Set

Table Number	Table Title	Population
Table 14.2.4.10	SDQ Subscale Hyperactivity/Inattention Score and Change from Baseline – Double Blind - Descriptive Statistics	FAS Set
Table 14.2.4.11	SDQ Subscale Hyperactivity/Inattention Score Change from Baseline at 13 Weeks Double Blind – MMRM Analysis	FAS Set
Table 14.2.4.12	SDQ Subscale Peer Relationship Problem Score and Change from Baseline – Double Blind - Descriptive Statistics	FAS Set
Table 14.2.4.13	SDQ Subscale Peer Relationship Problem Score Change from Baseline at 13 Weeks Double Blind – MMRM Analysis	FAS Set
Table 14.2.4.14	SDQ Subscale Prosocial Behaviour Score and Change from Baseline – Double Blind - Descriptive Statistics	FAS Set
Table 14.2.4.15	SDQ Subscale Prosocial Behaviour Score Change from Baseline at 13 Weeks Double Blind – MMRM Analysis	FAS Set
Table 14.2.5.1	Actigraphy Total Sleep Time and Change from Baseline – Double Blind - Descriptive Statistics	FAS Set
Table 14.2.5.2	Actigraphy Total Sleep Time Change from Baseline at 13 Weeks Double Blind – MMRM Analysis	FAS Set
Table 14.2.5.3	Actigraphy Sleep Latency and Change from Baseline – Double Blind - Descriptive Statistics	FAS Set
Table 14.2.5.4	Actigraphy Sleep Latency Change from Baseline at 13 Weeks Double Blind – MMRM Analysis	FAS Set
Table 14.2.5.5	Actigraphy Duration of Wake and Change from Baseline – Double Blind - Descriptive Statistics	FAS Set
Table 14.2.5.6	Actigraphy Duration of Wake Change from Baseline at 13 Weeks Double Blind – MMRM Analysis	FAS Set
Table 14.2.5.7	Actigraphy Number of Awakenings and Change from Baseline – Double Blind - Descriptive Statistics	FAS Set
Table 14.2.5.8	Actigraphy Number of Awakenings Change from Baseline at 13 Weeks Double Blind – MMRM Analysis	FAS Set
Table 14.2.5.9	Actigraphy Longest Sleep Period and Change from Baseline – Double Blind - Descriptive Statistics	FAS Set
Table 14.2.5.10	Actigraphy Longest Sleep Period Change from Baseline at 13 Weeks Double Blind – MMRM Analysis	FAS Set
Table 14.2.5.11	Actigraphy Sleep Efficiency and Change from Baseline – Double Blind - Descriptive Statistics	FAS Set
Table 14.2.5.12	Actigraphy Sleep Efficiency Change from Baseline at 13 Weeks Double Blind – MMRM Analysis	FAS Set
Table 14.2.6.1	SND Total Sleep Time Change from Baseline at 3 Weeks Double Blind – MMRM Analysis	FAS Set
Table 14.2.6.2	SND Total Sleep Time and Change from Baseline – Open Label - Descriptive Statistics	FAS Set
Table 14.2.6.3	SND Total Sleep Time Change from Baseline Analysis During the Open Label Phase	FAS Set
Table 14.2.6.4	SND Sleep Latency Change from Baseline at 3 Weeks Double Blind – MMRM Analysis	FAS Set
Table 14.2.6.5	SND Sleep Latency and Change from Baseline – Open Label - Descriptive Statistics	FAS Set
Table 14.2.6.6	SND Sleep Latency Change from Baseline Analysis During the Open Label Phase	FAS Set
Table 14.2.6.7	SND Duration of Wake Change from Baseline at 3 Weeks Double Blind – MMRM Analysis	FAS Set

Table Number	Table Title	Population
Table 14.2.6.8	SND Duration of Wake and Change from Baseline – Open Label - Descriptive Statistics	FAS Set
Table 14.2.6.9	SND Duration of Wake Change from Baseline Analysis During the Open Label Phase	FAS Set
Table 14.2.6.10	SND Number of Awakenings Change from Baseline at 3 Weeks Double Blind – MMRM Analysis	FAS Set
Table 14.2.6.11	SND Number of Awakenings and Change from Baseline – Open Label - Descriptive Statistics	FAS Set
Table 14.2.6.12	SND Number of Awakenings Change from Baseline Analysis During the Open Label Phase	FAS Set
Table 14.2.6.13	SND Longest Sleep Period Change from Baseline at 3 Weeks Double Blind – MMRM Analysis	FAS Set
Table 14.2.6.14	SND Longest Sleep Period and Change from Baseline – Open Label - Descriptive Statistics	FAS Set
Table 14.2.6.15	SND Longest Sleep Period Change from Baseline Analysis During the Open Label Phase	FAS Set
Table 14.2.6.16	SND Total Time in Bed Change from Baseline at 3 Weeks Double Blind – MMRM Analysis	FAS Set
Table 14.2.6.17	SND Total Time in Bed and Change from Baseline – Open Label - Descriptive Statistics	FAS Set
Table 14.2.6.18	SND Total Time in Bed Change from Baseline Analysis During the Open Label Phase	FAS Set
Table 14.2.6.19	SND TST Response – Logistic Regression	FAS Set
Table 14.2.6.20	SND Sleep Latency Response – Logistic Regression	FAS Set
Table 14.2.6.21	SND TST Response – Logistic Regression (Non-Missing Data)	FAS Set
Table 14.2.6.22	SND Sleep Latency Response – Logistic Regression (Non-Missing Data)	FAS Set
Table 14.2.6.23	SND Shift in Time to Bed by Scheduled Visit	FAS Set
Table 14.2.7.1	CSDI Sleep Disturbance Change from Baseline at 3 Weeks Double Blind – MMRM Analysis	FAS Set
Table 14.2.7.2	CSDI Sleep Disturbance and Change from Baseline – Open Label - Descriptive Statistics	FAS Set
Table 14.2.7.2	CSDI Sleep Disturbance Change from Baseline Analysis During the Open Label Phase	FAS Set
Table 14.2.8.1	CGAS Score Change from Baseline at 3 Weeks Double Blind – MMRM Analysis	FAS Set
Table 14.2.8.2	CGAS Score and Change from Baseline – Open Label - Descriptive Statistics	FAS Set
Table 14.2.8.2	CGAS Score Change from Baseline Analysis During the Open Label Phase	FAS Set
Table 14.2.9.1	SDQ Total Difficulties Score Change from Baseline at 3 Weeks Double Blind – MMRM Analysis	FAS Set
Table 14.2.9.2	SDQ Total Difficulties Score and Change from Baseline – Open Label - Descriptive Statistics	FAS Set
Table 14.2.9.3	SDQ Total Difficulties Score Change from Baseline Analysis During the Open Label Phase	FAS Set
Table 14.2.9.4	SDQ Impact Score Change from Baseline at 3 Weeks Double Blind – MMRM Analysis	FAS Set

Table Number	Table Title	Population
Table 14.2.9.5	SDQ Impact Score and Change from Baseline – Open Label - Descriptive Statistics	FAS Set
Table 14.2.9.6	SDQ Impact Score Change from Baseline Analysis During the Open Label Phase	FAS Set
Table 14.2.9.7	SDQ Subscale Emotional Symptoms Score Change from Baseline at 3 Weeks Double Blind – MMRM Analysis	FAS Set
Table 14.2.9.8	SDQ Subscale Emotional Symptoms Score and Change from Baseline – Open Label - Descriptive Statistics	FAS Set
Table 14.2.9.9	SDQ Subscale Emotional Symptoms Score Change from Baseline Analysis During the Open Label Phase	FAS Set
Table 14.2.9.10	SDQ Subscale Conduct Problem Score Change from Baseline at 3 Weeks Double Blind – MMRM Analysis	FAS Set
Table 14.2.9.11	SDQ Subscale Conduct Problem Score and Change from Baseline – Open Label - Descriptive Statistics	FAS Set
Table 14.2.9.12	SDQ Subscale Conduct Problem Score Change from Baseline Analysis During the Open Label Phase	FAS Set
Table 14.2.9.13	SDQ Subscale Hyperactivity/Inattention Score Change from Baseline at 3 Weeks Double Blind – MMRM Analysis	FAS Set
Table 14.2.9.14	SDQ Subscale Hyperactivity/Inattention Score and Change from Baseline – Open Label - Descriptive Statistics	FAS Set
Table 14.2.9.15	SDQ Subscale Hyperactivity/Inattention Score Change from Baseline Analysis During the Open Label Phase	FAS Set
